9.5.2 Analysis of primary endpoints

Phase I

Analysis of the primary safety endpoints (i.e., TEAEs, SAEs and DLTs) will be performed using the Safety Analysis Set (for TEAEs and SAEs) and the DLT Evaluation Set (for DLTs), respectively.

Descriptive statistics with number and proportion (%) of patients reporting at least one TEAEs in the following categories will be summarized by:

- DLTs
- Any TEAE
- Treatment-related TEAE
- Grade of TEAE
- Related Grade ≥3 TEAE
- Serious TFAF
- Treatment-related serious TEAE
- TEAEs leading to permanent discontinuation of trial treatment
- Fatal TEAEs

None of the Phase I safety endpoints will be formally tested so that the type I error rate will be preserved for Phase II primary endpoint of mDFS.

Page 89 of 127 Version: 2.0 Date: 22 JAN 2024

Phase II

For the Phase II part of this trial, the primary analyses will be performed using the Full Analysis Set (FAS) at two-sided 5% type I error rate. The analysis will be repeated using the Per Protocol (PP) set as sensitivity analyses. The time to DFS will be analyzed using Kaplan-Meier methodology by treatment group and censored in accordance with the FDA Guidance: "Clinical Trial Endpoints for the Approval of Cancer Drugs and Biologics" and the EMA guidance "Guideline on the evaluation of anticancer medicinal products in man". Censoring rules will be defined in the SAP.

The primary endpoint (mDFS) is defined as the time from randomization to occurrence of any of the following events, whichever occurs first:

- Locoregional recurrence or distant metastases as determined by an independent central radiology assessment.
- Occurrence of second primary (same or other) cancer as determined by an independent central radiology assessment.
- Death from any cause.

9.5.3 Analysis of secondary endpoints

The secondary endpoints are defined in Section 3.

The secondary efficacy analyses will be performed for both Phase I and Phase II parts. The full analysis set will be used and will be repeated using the PP set as sensitivity analyses.

Overall survival (OS)

OS is defined as the time from randomization to death from any cause.

The time to OS will be analyzed using Kaplan-Meier methodology by treatment group/cohort. Patients alive or patients lost to follow-up at date of analysis cut-off will be censored at the day of their last date known to be alive. Additional censoring rules will be defined in the SAP.

OS rate is defined as percentage of patients who are alive using the Kaplan-Meier methodology.

The OS rates in percentage will be presented by treatment and cohort at 12, 24, 36, and 48 months.

Disease-free survival (DFS)

DFS rates is defined as percentage of patients who are disease-free as defined in Section 9.5.2.

In addition to the primary analysis of time to DFS events the DFS rates in percentage will be presented by treatment and cohort at 12, 24, 36, and 48 months.

Page 90 of 127 Version: 2.0 Date: 22 JAN 2024

Relapse-free survival (RFS)

RFS is defined as the time from randomization to occurrence of any of the following events, whichever occurs first:

- Locoregional recurrence or distant metastases as determined by the investigator.
- Death from any cause.

The following are considered as events: locoregional recurrence, distant metastases, death from PDAC, death from other cancer, non-cancer death, treatment-related death. Occurrence of second primary (same or other) cancer as determined by the investigator are ignored. Patients still event-free or patients lost to follow-up at date of analysis cut-off will be censored at the day of their last date known to be event-free. Additional censoring rules may be defined in the SAP.

RFS will be analyzed using Kaplan-Meier methodology by treatment group.

Analysis of secondary efficacy endpoints

Pharmacokinetic (PK)

The PK analysis will be performed based on Pharmacokinetic Set (PK Set).

Individual and mean (\pm standard deviation) serum concentration of BNT321 when coadministered with mFOLFIRINOX will be tabulated and plotted over time. PK parameters will be estimated from the serum concentration data using a non-compartmental analysis method. PK parameters will include C_{max} , t_{max} , $t_{1/2}$, Vd, AUC, and CL. These parameters will be listed by individual patient and summarized using descriptive statistics (means, medians, ranges, standard deviations, and coefficient of variation as appropriate).

Immunogenicity

The immunogenicity analysis will be performed based on FAS.

Immunogenicity results will be listed by patient, and a summary will be provided by the number and percentage of patients who develop detectable anti-BNT321 antibodies. The immunogenicity titre and neutralising ADA data will be listed for samples confirmed positive for the presence of anti-BNT321 antibodies.

The effect of immunogenicity as well as the effect of its neutralising properties on PK, pharmacodynamics, efficacy, and safety will be evaluated, if the data allow.

Pharmacodynamic (PD)

The PD analysis will be performed based on Pharmacodynamic Set (PD Set).

The percentage of lysis of target positive cells via patient-derived effector cells as a readout for ADCC activity, and/or patient-derived serum containing antibody and/or complement as a readout for CDC activity will be summarized by visit. Other PD parameters may be summarized if sufficient data is available.

Page 91 of 127 Version: 2.0 Date: 22 JAN 2024

Heath-related quality of life (EORTC QLQ-C30 and QLQ-Pan26)

The analysis of health-related quality of life analysis will be performed based on FAS. The EORTC QLQ-C30 and EORTC QLQ-Pan26 will be scored according to the EORTC Scoring Manual (Fayers et al. 2001). An outcome variable consisting of a score from 0 to 100 will be derived for each of the symptom scales, each of the functional scales, and the global measure of health status scale according to the EORTC Scoring Manual. Higher scores on the global measure of health status and functional scales indicate better health status/function, but higher scores on symptom scales represent greater symptom severity. For each subscale, if at least 50% of the subscale items have been answered, then the subscale score can be calculated. The subscale score will be divided by the number of non-missing items and multiplied by the total number of items on the subscales (Fayers et al. 2001). Otherwise, the subscale will be treated as missing. Missing single items are treated as missing. The reason for any missing questionnaire will be identified and recorded.

The main PRO measures identified in the secondary objectives are global health status/QoL, EORTC QLQ-C30 (includes physical functioning, fatigue, pain and appetite loss subscales). For EORTC QLQ-Pan26, one subscale (e.g. pancreatic pain) will be identified as part of the main analysis of the secondary endpoint. In addition, separate analysis may be conducted for each EORTC QLQ-Pan26 scale/symptom score.

The primary assessment of global health status/QoL, physical functioning, or symptom will focus on comparing mean change from baseline at end of Cycle 12 between treatment arms. Change from baseline at end of Cycle 12 will be analyzed using a mixed model repeated measurements analysis of post-baseline scores. The model will include treatment arm, visit, and treatment by visit interaction as explanatory variables, and the baseline score and baseline score by visit interaction as covariates. Adjusted mean change from baseline at end of Cycle 12 estimates per treatment arm and corresponding 95% CIs will be presented, along with an overall estimate of the treatment difference, 95% CI, and p-value. In addition, differences in LSMeans at end of Cycle 12 between treatments together with 95% CIs as well as standardized mean differences will be presented.

Summary tables of responses for each EORTC QLQ-C30 and EORTC QLQ-Pan26 scale/item score (global health status/QoL, 5 functions, fatigue, pain, appetite loss) for each assessment (improvement, deterioration, and no change) will be presented by treatment arm.

Finally, summaries of absolute and unadjusted change from baseline at end of Cycle 12 values of each

EORTC QLQ-C30 and EORTC QLQ-Pan26 scale/item score will be reported by assessment timepoint for each treatment arm. Graphical presentations may also be produced as appropriate.

Full details of the statistical analyses and appropriate sensitivity analyses will be described in full in the SAP.

Page 92 of 127 Version: 2.0 Date: 22 JAN 2024

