4.2.2 Trial design rationale for Phase II: Randomized mFOLFIRINOX ± BNT321

The randomized Phase II part of this trial is designed as a dedicated evaluation of the potential for BNT321 combination therapy with mFOLFIRINOX to provide meaningful clinical benefit to patients with R0 or R1 surgically resectable PDAC. mFOLFIRINOX, the selected regimen for combination and the comparator arm for BNT321-02, is considered a superior option to gemcitabine + nab-paclitaxel for PDAC adjuvant therapy based on results of Phase III PRODIGE 24 and APACT studies (Conroy et al. 2018 and Tempero et al. 2022 respectively). The BNT321-02 Phase II design employs several parameters from the pivotal Phase III PRODIGE 24 study.

DFS is selected as the primary endpoint for the randomized Phase II part of this trial. This is an established, clinically meaningful outcome previously used as primary endpoint in the PRODIGE 24 and APACT Phase III trials. A substantial improvement in mDFS is sought in trial BNT321-02, specifically a greater than 12 months increase with the introduction of Q2W BNT321 to the 24-week mFOLFIRINOX chemotherapy standard (target 36 vs 21.6 months DFS, hazard ratio [HR] 0.60).

In addition to primary endpoint mDFS, additional outcome measures evaluated as secondary endpoints include 12 months DFS and OS at 24 months. The mFOLFIRINOX 12 months DFS rate of 69.0% observed in PRODIGE 24 is a high efficacy benchmark, but a significant DFS improvement at this timepoint in BNT321-02 would represent a major efficacy advance and may be a consideration for accelerated registration. Overall survival assessment at 24 months is in a feasible timeframe relative to the trial mDFS primary endpoint and may provide additional supportive efficacy data in this first BNT321 adjuvant trial.

The randomized Phase II part of this trial will be conducted in an open-label fashion, consistent with design of other major adjuvant studies (Tempero et al. 2022). Another notable design consideration is inclusion of stratifications for surgical resection status (R0 versus R1) and nodal status at time of resection (pN0 versus pN1). Both of these resection characteristics are recognized as significant factors in clinical outcome in resected PDAC and so are justified for stratification in the BNT321-02 trial design, similar to an approach in previous PDAC adjuvant studies (Conroy et al. 2018).

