6.6.2 Randomization

For Phase II, part 2, patients will be randomized in a 1:1 fashion to one of two treatment arms, mFOLFIRINOX + BNT321 or mFOLFIRINOX alone. Randomization will be conducted in the trial's interactive web response system (IWRS) up to 3 days before Cycle 1 Day 1. Randomization will include stratifications to ensure balanced enrollment between the two arms for the following characteristics: tumor resection status (R0 vs R1) and tumor nodal status at resection (pN0 vs pN1).

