9.5.1 General considerations

In general, the statistical analyses will be performed for Phase I and Phase II parts separately. The Phase I part analysis will be performed by dose level cohort. The Phase II part will be performed by treatment group (i.e., mFOLFIRINOX + BNT321 and mFOLFIRINOX).

Continuous variables will be summarized by treatment group/cohort using the following descriptive statistics: number of patients (n), mean, standard deviation, median, minimum and maximum

Categorical variables will be summarized by treatment group/cohort presenting absolute and relative frequencies (n and %) of patients in each category.

Time-to-event-endpoints will be analyzed using Kaplan-Meier methodology by treatment group/cohort and censored in accordance with the FDA Guidance: "Clinical Trial Endpoints for the Approval of Cancer Drugs and Biologics" and the EMA guidance "Guideline on the

Page 88 of 127 Version: 2.0 Date: 22 JAN 2024

evaluation of anticancer medicinal products in man". Censoring rules will be defined in the SAP.

The median survival time (including two-sided 95% confidence limits according to Brookmeyer and Crowley) and the first and third quartile will be presented for each treatment group/cohort. Survival rates and DFS rates (including two-sided 95% confidence interval based on the Greenwood 1926 formula) as well as the number and percentage of patients with events, censored and under risk will be displayed for selected time points (e.g., at 12, 24, 36 and 48 months).

The survival distributions for two treatment groups will be compared using the stratified log-rank test (stratified by the stratification factors surgical resection status and nodal status at time of resection), and the p-value will be provided. The associated HR and two-sided 95% confidence interval will be estimated by using stratified (i.e., R0 versus R1; pN0 versus pN1) Cox proportional hazard model with treatment as model covariate.

The time-to-event analysis will be illustrated using Kaplan-Meier plots by treatment group and additionally strata. Baseline is defined as last available value prior to randomization (Phase II)/first dose of IMP (Phase I).

Data up to and including the clinical cut-off date for the statistical analysis will be included in the statistical analysis. Handling of missing data will be described in the SAP.

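### The HRQoL mixed model leaves out the two randomization factors; if they predict HRQoL beyond the baseline score, its confidence interval and p-value are slightly conservative

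*Combined protocol and SAP*

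**What the plan says.** Section 6.6.2 of the protocol sets up 1:1 allocation in Phase II and says "Randomization will include stratifications to ensure balanced enrollment between the two arms for the following characteristics": resection status (R0 versus R1) and nodal status (pN0 versus pN1). Section 9.5.1 carries both factors into the comparison of survival distributions, with a log-rank test "stratified by the stratification factors surgical resection status and nodal status at time of resection" and a Cox model stratified in the same way.

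The HRQoL part of Section 9.5.3 describes a different kind of model. Its main target is "comparing mean change from baseline at end of Cycle 12 between treatment arms". The terms are listed one by one: "The model will include treatment arm, visit, and treatment by visit interaction as explanatory variables". The only covariates named after that are each patient's score at baseline and its interaction with visit. The output is an adjusted arm difference with a 95% confidence interval and a p-value. Neither randomization factor is among the terms, and no reason is given. The section closes by leaving full details and sensitivity analyses to the SAP; the supplied document contains no separate SAP text.

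**The concern.** Stratified randomization balances the strata between arms, so stratum differences contribute almost nothing to the sampling variability of the arm difference. A model without the strata does not know this. It leaves their variance in the residual and calculates its standard error as if allocation had ignored them. If the strata predict the outcome, the reported standard error is then larger than the true one, the interval is too wide and the p-value too large.

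What is at stake is the reported precision of one secondary comparison, for which the plan commits to an interval and a p-value. The protocol gives some reason to expect that the factors could matter. Section 4.2.2 justifies stratifying by them with the words "Both of these resection characteristics are recognized as significant factors in clinical outcome in resected PDAC". That statement concerns clinical outcome, however, and HRQoL is not mentioned.

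**Working it through.** **The plan's own figure.** No sample size, standard deviation or effect size is given for HRQoL. The only sizing figure is the 164 disease-free survival events in Section 9.3 (hazard ratio 0.60, two-sided 5%, power 90%). Schoenfeld's formula gives 4(1.960 + 1.282)² / (ln 0.60)² = 4 × 10.51 / 0.2609 ≈ 161.1, rounded up to 162. Power at 164 events is 90.5%. The figure reproduces, and nothing in it depends on the HRQoL model.

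**Inputs.**
- Model terms: Section 9.5.3.
- Strata and 1:1 allocation: Section 6.6.2.
- Phase II size of 300: Section 9.3.
- R², the share of residual HRQoL variance (after the baseline score) that the two factors explain: not in the documents. It is assumed, with a range of 0 to 0.10.

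**Formulas.**
- Standard error with strata divided by standard error without: sqrt(1 − R²).
- Extra width of the interval when strata are omitted: 1/sqrt(1 − R²) − 1.
- Actual two-sided rejection rate under the null when strata are omitted but balanced by design: 2[1 − Φ(1.96/sqrt(1 − R²))].

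| Assumed R² | SE ratio | Interval wider by | Actual rate at nominal 5% |
|---|---|---|---|
| 0 | 1.000 | 0% | 0.050 |
| 0.01 | 0.995 | 0.5% | 0.049 |
| 0.02 | 0.990 | 1.0% | 0.048 |
| 0.05 | 0.975 | 2.6% | 0.044 |
| 0.10 | 0.949 | 5.4% | 0.039 |

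Doubling the top of the range to 0.20 would give 11.8%.

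**Check by simulation.** The setting was 300 patients, no true arm effect, 4,000 runs per row, and an analysis of covariance with baseline score at one time point. Permuted blocks of 4 within strata and stratum prevalences of 40% and 70% are assumptions. Each cell shows strata omitted / strata included.

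| R² | Reported SE | Empirical SE | Rejection rate |
|---|---|---|---|
| 0 | 0.1155 / 0.1155 | 0.1175 / 0.1175 | 0.0548 / 0.0537 |
| 0.02 | 0.1156 / 0.1144 | 0.1119 / 0.1119 | 0.0428 / 0.0445 |
| 0.05 | 0.1155 / 0.1126 | 0.1109 / 0.1109 | 0.0393 / 0.0447 |
| 0.10 | 0.1156 / 0.1096 | 0.1091 / 0.1090 | 0.0395 / 0.0493 |

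The Monte Carlo error of a rejection rate near 5% is sqrt(0.05 × 0.95 / 4000) = 0.0034, so 0.0548 in the first row is compatible with 0.05.

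Two things follow. The empirical standard error is practically the same with and without the strata, because the randomization has already delivered the gain. Only the reported standard error differs: at R² = 0.10 it is 0.1156 / 0.1096 = 1.055 times as large without the strata, in line with the formula.

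**The case against.** **Section 9.5 is a summary.** Section 9.5 describes itself as a summary, the HRQoL text leaves full details to the SAP, and Section 9 allows the SAP to modify the protocol's outline. The strata could therefore still be added. This is true, but Section 9.5.3 goes beyond a summary by listing the model's terms. An SAP author who follows that list will leave the strata out.

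**There may be no loss at all.** This stands. If resection and nodal status do not predict HRQoL once the baseline score is in the model, omission costs nothing. Section 4.2.1 says that most relapses come after the first six months following surgery, and end of Cycle 12 is 12 × 14 = 168 days, or 24 weeks, after treatment starts. If the strata act on HRQoL mainly through relapse (an inference, not something the protocol says), much of their effect would come later. A reader might infer that the plan definitely gives precision away; the documents do not show that.

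**No information is lost.** This also stands. A reader might translate the wider interval into a percentage of the sample lost. The simulation does not support that: the estimate itself is as precise either way, and only its reported uncertainty is conservative.

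**The plan does not contradict itself.** A reader might see an inconsistency with the time-to-event analyses. Section 9.5.1 prescribes stratification for those comparisons only, and no passage promises it for the mixed model. This is a difference between endpoint types.

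**Conclusion.** The omission is plain on the page. Its consequence is conditional and small. For an assumed R² of 0 to 0.10, the interval for the HRQoL arm difference is 0% to 5.4% wider than with the strata included, and a nominal 5% test rejects at about 5.0% down to 3.9% under the null. The error is on the conservative side, with no bias and no inflation of type I error. The disease-free survival test, the 164 events and the 300 patients are untouched.

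The range rests on the assumed R², for which the documents offer no figure, and on near-perfect balance of the strata through the randomization. The simulation used a single time point and not the full repeated-measures model. This is a minor point, worth making because the correction costs so little.

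**What to change.** Add resection status (R0/R1) and nodal status (pN0/pN1) as fixed effects to the HRQoL mixed model, in Section 9.5.3 and in the SAP. The cost is one line of text and about two degrees of freedom in roughly 300 patients. In the simulation, including the factors when they explained nothing left the reported standard error at 0.1155. No data collection changes, because both factors are needed for randomization anyway. Section 9.5 has the SAP finalized before the first database lock for the primary analysis. In an open-label trial it is better to settle the covariates now, so that they cannot look like a later choice. If the sponsor prefers the model as listed, a sentence giving the reason would do.

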9.5.4 Analysis of safety data

Safety data that will be summarized includes AEs, clinical laboratory parameters, vital signs, and ECGs. All safety analyses will be based on the Safety Analysis Set and will be summarized descriptively by treatment group Phase II/cohort Phase I unless otherwise stated.

Adverse events

AEs will be coded using the most recent version of Medical Dictionary for Regulatory Activities (MedDRA®) coding system to get a System Organ Class (SOC) and Preferred Term (PT) for each AE and graded for severity using NCI CTCAE v5.0.

A treatment-emergent AE is defined as any AE with an onset date on or after the first administration of IMP (if the AE was absent before the first administration of IMP) or worsened after the first administration of IMP (if the AE was present before the first administration of IMP). AEs with an onset date more than 28 days after the last administration of IMP will be considered as treatment-emergent only if assessed as related to IMP by the investigator.

Treatment-emergent AEs (as defined in Section 10.4.1) will be summarized overall and by treatment group Phase II/cohort Phase I.

The number and percentage of patients reporting at least one AE will be summarized by PT nested within SOC for each of the following AE types:

- Any AE
- Related AE
- Grade ≥3 AE
- Related Grade ≥3 AE
- Any SAE
- Related SAE
- · SAE leading to death
- AEs leading to dose reduction
- AE leading to permanent discontinuation of treatment
- DLT (Phase I only)
- AESIs

Moreover, the number and percentage of patients with any AE will be summarized by worst NCI CTCAE grade by PT nested within SOC.

For Phase I only, DLTs will be presented in terms of listings presenting the reported term and MedDRA PT and SOC term, its time of onset, duration, and outcome, relationship, NCI CTCAE grade, and seriousness including dose exposure data.

Page 93 of 127 Version: 2.0 Date: 22 JAN 2024

Laboratory parameters

Clinical laboratory assessments to be summarized include hematology, blood chemistry, and urinalysis. The clinical laboratory parameters to be assessed are listed in Section 8.3.4 and at the time points specified in the SoA (Section 1.3).

Clinical laboratory parameters at each timepoint and change from baseline to each postbaseline timepoint will be summarized using descriptive summary statistics for each parameter by treatment group Phase II/cohort Phase I.

Clinical laboratory results will be classified according to the most recent version of NCI CTCAE. Shift tables from baseline to worst grade on-treatment will be provided for each laboratory parameter by treatment group Phase II/cohort Phase I.

Additionally, the occurrence of clinically significant abnormal laboratory results within a patient will be analyzed using descriptive summary statistics for each parameter and visit by treatment group Phase II/cohort Phase I.

Laboratory results will be listed along with the normal ranges and NCI CTCAE grade. Laboratory values that are below or above the normal ranges will be flagged.

Vital signs

Vital sign parameters to be assessed are listed in Section 8.3.2 and at the time points specified in the SoA (Section 1.3).

Vital sign parameters at each timepoint and change from baseline to each post-baseline timepoint will be summarized using descriptive summary statistics for each parameter by treatment group Phase II/cohort Phase I.

Additionally, the occurrence of abnormal vital sign results within a patient will be analyzed using descriptive summary statistics for each parameter and visit by treatment group Phase II/cohort Phase I.

ECG

ECG parameters to be assessed are listed in Section 8.3.3 and at the time points specified in the SoA (Section 1.3).

ECGs will be judged by the investigator as clinically significant (yes/no). The number and percentage of patients with clinically significant ECG findings will be summarized by treatment group Phase II/cohort Phase I for each visit.

